5.6.2. Analysis of Secondary Efficacy Variables

The time to EAR for Cat Allergen Challenges on days 29, 57, and 85 will be evaluated in a similar way to the primary analysis.

The change and percent change from the Baseline Controlled Cat Allergen Challenge in AUC of FEV1 (L) during the Controlled Cat Allergen exposure will be calculated and analyzed by mixed-effect model repeated measures (MMRM) with the treatment, visit, and treatment-by-visit interaction as factors and the AUC of FEV1 during the baseline Controlled Cat Allergen Challenge, time to EAR during the baseline controlled cat allergen challenge, and allergen concentration in the EEU for each visit as continuous covariates. The primary method for the calculation of the AUC is described in Section 6.2, where last observation carried forward (LOCF) is used to calculate the AUC from 0 to 2 hours. An unstructured covariance structure will be utilized; if the model does not converge, an autoregressive structure will be employed. Between-group estimates and nominal p values will be reported for Controlled Cat Allergen Challenges on days 8, 29, 57, and 85. Missing data from Controlled Cat Allergen Challenges on days 8, 29, 57, or 85 will be accounted for via MMRM. The change from the Baseline Challenge in AUC of TNSS and TOSS will be analyzed in a similar manner.

The change and percent change in cat allergen quantity (tolerated exposure) from the baseline Cat Allergen Challenge, will also be analyzed using a similar MMRM model with the treatment, visit, and treatment by-visit interaction as factors and the cat allergen quantity tolerated in the baseline Controlled Cat Allergen Challenge as a covariate.

As a sensitivity analysis the AUC for each endpoint will also be calculated during the period of time where the patient was in the EEU (adjusted for the exposure interval) to give the average value of FEV1, TNSS, and TOSS during the EEU exposure. An MMRM model will be used to model the change (and percent change for FEV1) from the Baseline Challenge in the average value during the EEU exposure. An additional sensitivity analysis will be performed, where the AUC will also be calculated from 0 to 4 hours with LOCF at post-randomization Cat Allergen Challenges following the method outlined in Section 6.2. An MMRM model will be used to model the AUC at each visit (rather than the change in AUC), adjusting for the Baseline Challenge AUC in addition to the time to EAR in the baseline challenge test and the allergen concentration in the EEU. A similar analysis looking at the AUC from 0 to 2 hours with LOCF will also be performed, modeling the raw AUC values at each visit rather than the percent change from baseline.

Subgroup analyses will be performed for the change in AUC of TNSS and TOSS for patients who had a non-zero baseline AUC value and in patients who attained a TNSS of at least 3 during the EEU challenge at baseline.

5.6.3. Analysis of Other Efficacy Variables

The time to LAR at each of the Controlled Cat Allergen Challenges in an EEU will also be explored. After the allergen challenge (when the patient exits the EEU), the patient is observed

onsite for 6 hours and then for an additional 18 hours at home. If a patient does not experience an LAR within the 24-hour period, their time to LAR will be censored at 24 hours.

The time to LAR will be defined as the time to a $\geq 15\%$ reduction in FEV1 during the 6-hour onsite observation period (adjudicated by the blinded investigators). During the at-home monitoring period up to 24 hours after the patient exits the EEU, the time to LAR will be defined as the time to a $\geq 15\%$ reduction in FEV1 (confirmed by two spirometry efforts within 5 minutes) along with either rescue medication use (any medication at any dose) within 1 hour or the presence of chest symptoms within 1 hour of the drop in FEV1 (adjudicated by the blinded investigators). Chest symptoms are identified by a response of Mild, Moderate or Severe to the chest symptom questions involving chest tightness, wheezing, cough, throat tightness, and difficulty breathing. Multiple asthma exacerbations during the observation period or at-home monitoring period within the same patient may be adjudicated by the site to be an extended LAR (no more than one LAR within 24 hours of leaving the EEU may be adjudicated, e.g. a subject cannot have more than one LAR within 24 hours of leaving the EEU).

The time to LAR for each treatment will be examined using Kaplan Meier estimates with patients being censored at 24 hours if they did not experience an LAR. The median time to LAR for each treatment group and the corresponding 95% confidence intervals will be presented for each Controlled Cat Allergen Challenge. A formal comparison of time to LAR in the treatment groups at each EEU challenge visit will be performed using a Cox proportional hazards model, adjusting for allergen concentration in the EEU. The Kaplan Meier and Cox Proportional Hazards models will be fit separately on the subgroup of patients who receive rescue medications upon EEU exit and for patients who do not. In patients who receive EEU related medications (including medications given on-site and rescue medications taken at-home), the impact of the carryover of medications between challenges will be explored by including taking medication or not as baseline variable for the model of each subsequent visits. A one-sided statistical test of the hazard ratio for placebo compared to drug will be performed.

The ratio of Fel d 1 IgE to Cat Allergen IgE at baseline will also be explored as potential covariate in the Cox Proportional Hazards model and will be log transformed if necessary.

If the Cox proportional hazards model does not converge, an extended Wilcoxon Rank Sum test comparing the ranks of time to LAR, adjusted by the covariates specified above, will be used ([LaVange and Koch, 2006](#)).

A time-to-event analysis with competing risks may also be used to examine the incidence of LAR, where the use of rescue medications upon EEU exit is treated as a competing risk with allergen concentration as a covariate in the model. The comparison of LAR-specific and rescue medication-specific cumulative incidences within 24 hours of an EEU challenge across treatment groups will be performed using Gray's method. The model will be fit for each EEU Challenge visit.

As an additional sensitivity analysis, the presence or absence of an LAR within the 24-hour period in the REGN1908-1909 treatment group as compared to placebo will be tested using a Fisher's Exact Test.

The time course of asthma response comprising both EAR and LAR will also be visualized and summarized. A similar analysis will be repeated for the time to any Asthma Reaction. The first asthma reaction that occurs, whether it occurs while the patient is in the EEU, in the on-site 6-

hour observation period, or in the at-home monitoring period, will be treated as the event time. If the subject experiences no asthmatic reaction at a given Allergen Challenge visit, the patient's time will be censored at 24 hours. Kaplan-Meier estimates and curves will be produced for each visit.

The presence or absence of any asthma exacerbation (EAR or LAR) in the REGN1908-1909 treatment group as compared to placebo will be tested using a Fisher's Exact Test.

Individual spaghetti plots and mean plots of the percent change in FEV1 over time will also be examined. LOCF will be used in the calculation for any graphical displays of the mean change in FEV1 over the Cat Allergen Challenge.

The peak TNSS and TOSS and change from pre-challenge baseline to peak TNSS and TOSS across EEU challenge visits may also be examined using MMRM models.

The change and percent change from the Baseline Cat Allergen Challenge in the Fractional exhaled Nitric Oxide (FeNO) (adjusted for the pre-challenge baseline) will be explored using an MMRM model, with the treatment, visit, and treatment by visit interaction, and use of steroid rescue medications within 24 hours of the EEU challenge as factors. The time in EEU will be included as a covariate in the model.

The skin prick test with serial allergen titration with cat allergen will also be compared between treatment groups using an MMRM model, with the treatment, visit and treatment by visit interaction as factors.

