During the Cat Allergen Challenge, standardized cat allergen extract (40 ng/m^3) is continuously nebulized into the EEU and patients perform spirometry every 10 minutes until they experience bronchoconstriction, when their FEV1 is reduced by  $\geq 20\%$ , defined as an EAR. Patients leave the EEU once they achieve an EAR, and they are then monitored outside of the EEU in an observation room for 6 hours. Patients who fail to achieve an EAR within 2 hours in the baseline Cat Allergen Challenge in the EEU will be excluded from the study. During the time they are in the EEU, they record their TNSS, a validated, patient-reported, composite symptom assessment of congestion, itching, rhinorrhea, and sneezing, and TOSS, a validated, patient-reported, composite symptom assessment of ocular symptoms (itching, redness, tearing, and swelling) using handheld tablets every 20 minutes. During the 6-hour observation

---

---

period after leaving the EEU, FEV1 is measured every 30 minutes to assess for a late asthmatic response (LAR), defined as a delayed drop of 15% after exiting the EEU. During the 6-hour observation period, TNSS, TOSS, and chest symptom questions are recorded every hour. At the end of the 6-hour monitoring period, patients are discharged home if FEV1  $\geq$ 90% of the baseline value; if FEV1 is <90% of the baseline value, patients will continue to be monitored at the clinic until the patient meets criteria for discharge. FEV1 is monitored during 6 hours after the EEU session using portable spiroometers, and patients are followed up 18 hours after leaving the clinical unit. Patients meeting eligibility criteria are randomized to a single dose of REGN1908-1909 (600 mg SC) or placebo. Patients then return to the study site to undergo a 4-hour Cat Allergen Challenge in the EEU on days 8, 29, 57, and 85 with a 6-hour observation period, at which time EAR, TNSS, and TOSS are assessed using the same time points that were used at baseline. Exploratory measures are also assessed at baseline and throughout the study, as detailed in the exploratory objectives section.

---

Study Duration	The duration of the study for a patient is approximately 16 weeks, excluding the screening period.
End of Study Definition	The end of study for this study is defined as the last visit of the last patient.
Population	
Sample Size:	Approximately 60 patients with GINA 1 asthma sensitized to cat allergen.

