**8.1.1. Footnotes for the Schedule of Events Table**

1. All screening-related procedure should be performed between day -85 to -14
2. Randomization/study drug administration (visit 5) must occur within 14 to 28 days of visit 3.
3. Controlled Cat Allergen Challenge is performed as described in the study manual.
4. Screening Skin prick test for cat hair and skin prick testing for other common allergens is performed as described in the study manual. If screening skin prick test for cat hair is negative at screening visit 1 (mean wheal diameter less than at least 5 mm greater than a negative control), then other screening visit 1 procedures do not need to be performed as the patient will have failed screening based upon cat hair skin prick testing (eg, perform skin prick testing prior to other allergen skin prick testing, blood draw, spirometry, etc).
5. At screening visit 1, a spirometry session will be completed to check for FEV1 inclusion criteria. At visit 2, spirometry will be performed at baseline prior to the placebo EEU challenge, and then every 10 minutes during the placebo challenge, then every 30 minutes in the supervision room for 6 hours. On the Cat Allergen Challenge visits (3, 6, 7, 9, and 10) spirometry will be performed at baseline prior to entry into the EEU, every 10 minutes during the EEU exposure, every 30 minutes in the observation room for 6 hours after leaving the EEU, and then every hour for up to 18 hours after leaving the clinical unit except during sleeping. At visit 5, on the day of randomization, a spirometry session will be performed twice: once prior to receiving the study drug and once prior to leaving the clinical trial unit. Additional spirometry may be performed when prompted by asthma symptoms.
6. TNSS, TOSS, and chest symptom questions are assessed prior to Cat Allergen Challenge, approximately every 20 minutes during the challenge in the exposure unit, every 1 hour for 6 hours post-challenge while patients are being observed in the observation room, and then every 2 hours up to 18 hours after leaving the clinical unit, while they are home, except for the time that they are sleeping. Further details are provided in the study manual.
7. PNIF is assessed prior to Cat Allergen Challenge, approximately at the time of the EAR, and approximately 6 hours post-challenge while patients are being observed in the observation room. Further details are provided in the study manual.

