#### **8.2.2.3. Chest Symptoms Questions**

Individual respiratory symptoms of chest tightness/shortness of breath/trouble breathing, wheezing, and coughing are evaluated on a 4-point Likert scale ranging from 0 (none) to 3 (severe).

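### Time to LAR and time to any asthmatic reaction are censored at a flat 24 h, even for patients whose home FEV1 readings stopped early or were never taken

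*SAP*

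**What the plan says.** **Censoring.** SAP 5.6.3 describes follow-up after exit from the environmental exposure unit (EEU) as "onsite for 6 hours and then for an additional 18 hours at home". The censoring rule is: "If a patient does not experience an LAR within the 24-hour period, their time to LAR will be censored at 24 hours". The Kaplan-Meier paragraph repeats it, with "patients being censored at 24 hours if they did not experience an LAR". Later in the section, patients with no asthmatic reaction of any kind are also censored at 24 h. None of these statements refers to the last FEV1 reading. Time to LAR gets Kaplan-Meier estimates, a one-sided Cox test at each challenge, and Fisher's test on presence of an LAR within 24 h. A further Fisher's test covers any EAR or LAR.

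**Home data.** Under Protocol 8.1.1, footnote 5, spirometry continues after the observation room "and then every hour for up to 18 hours after leaving the clinical unit except during sleeping". Under footnote 6, chest questions continue "and then every 2 hours up to 18 hours after leaving the clinical unit, while they are home", again except during sleep.

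**Event definition.** The Protocol synopsis describes an LAR as "defined as a delayed drop of 15% after exiting the EEU". The SAP uses a fall of at least 15% on site. At home the fall must be "confirmed by two spirometry efforts within 5 minutes) along with either rescue medication use (any medication at any dose) within 1 hour", or be accompanied by chest symptoms within the same limit instead of rescue use. Blinded investigators adjudicate. On the instrument, Protocol 8.2.2.3 says: "Individual respiratory symptoms of chest tightness/shortness of breath/trouble breathing, wheezing, and coughing are evaluated". The SAP's list for the LAR rule also names throat tightness.

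**The concern.** A censoring time should mark the end of observation. An LAR can be seen only through FEV1 readings, so a patient who stops blowing into the home spirometer is no longer under observation for this endpoint. A flat 24 h keeps that patient in every later risk set and makes missing data look like a good outcome. The Kaplan-Meier curves, the Cox comparisons and both Fisher's tests inherit this at all four challenges.

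The SAP applies the right principle elsewhere. Under 5.6.1, a patient who leaves the EEU before an EAR for non-clinical reasons is censored at departure. LAR has no counterpart. SAP 6.3 does not fill the gap, because for efficacy it points only to rules for primary and secondary variables, and SAP 4.5.3 lists LAR as exploratory.

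A second, smaller worry is that the home definition relies on a repeat effort that the documents do not require.

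**Working it through.** **1. The plan's own figure.** 6 h on site + 18 h at home = 24 h. This reproduces the SAP's window.

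**2. Credit to a patient with no home readings.** The last FEV1 is at about 6 h. Unobserved time counted as LAR-free = 24 - 6 = 18 h, and 18/24 = 75% of the window.

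**3. Effect on the risk set.** Suppose d home LARs occur at a time when the SAP counts n patients at risk, of whom k have stopped recording. The SAP's Kaplan-Meier step is d/n. The observed risk set gives d/(n - k). The SAP's step is therefore (n - k)/n of the observed one. The documents give no value for k. As an assumed range, with n = 30 (one full arm):
- k = 3: 27/30 = 0.90
- k = 6: 24/30 = 0.80

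**4. Time to any asthmatic reaction.** Only patients without an EAR depend on readings after exit. Assume exponential times with the planning medians in Protocol 10.2 (58 and 132 min). The proportion without an EAR at 240 min is then:
- placebo: 2^(-240/58) = 0.06, or about 1.7 of 30
- active: 2^(-240/132) = 0.28, or about 8.5 of 30

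The flat rule can therefore reach only a minority of patients in this analysis. For time to LAR it can reach any patient without an LAR.

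**5. Sleep.** The documents give no sleep duration. Assuming 6 to 9 h, the share of the window without scheduled readings is 6/24 = 25% to 9/24 = 38%. Most of this is not changed by censoring at the last reading. Assume EEU entry at 09:00 and sleep from 23:00 to 07:00. After exit at 10:00 the window closes at 10:00 next day, 3 h after waking. After exit at 13:00 it closes at 13:00, 6 h after waking. If hourly readings resume on waking, the last valid reading is close to 24 h in both cases.

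**6. Confirmation within 5 minutes.** Scheduled home readings are 60 min apart, so no two scheduled time points can confirm each other. The second effort must come from the same session or from an extra reading. Extra readings are optional and symptom-prompted (Protocol 8.2.2.4). The automatic alarm is set at a 30% fall (Protocol 7.4). No stated trigger therefore produces a repeat for a fall of 15-30%.

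**7. Symptoms within 1 hour.** Place FEV1 at home hours 1 to 18 and chest questions at hours 2, 4, ..., 18. All 18 readings have a symptom entry within 1 h, and 9 of 18 coincide. If the two grids are shifted against each other, a two-sided window still covers 94-100% of readings. A forward-only window can fall to about 44%. The SAP does not say which is meant.

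**The case against.** The strongest reply is that the stricter home rule is deliberate. Unsupervised readings are noisier, confirmation removes false falls, and adjudication is blinded. The protocol's 15% description is attached to the 6-hour observation period, so the SAP is not clearly departing from a home definition. Two efforts in one session would satisfy the 5-minute rule. SAP 4.5.2 foresees several efforts at one time point, and the operations manual, which is not available here, may require them. All of this stands. It is why the confirmed definition should remain the main one, and why the point is only that neither document requires the second effort.

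The reply also notes that LAR is exploratory and that the validation study's mean time to LAR was 180 minutes, within the on-site period. That limits the consequence. It does not justify a censoring time that ignores when observation ended.

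A reader might infer that symptom data are not called for at home, or are available only about half the time. The documents do not support this: chest questions are scheduled every 2 h while awake, and step 7 shows near-complete coverage unless the window is forward-only and the schedules are offset.

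**Conclusion.** The censoring rule should be changed. As written, it credits up to about 18 h of unobserved time as LAR-free and scores patients without home readings as having no LAR. This rests on reading the rule literally: no exception for missing home readings appears in SAP 5.6.3 or 6.3. How many patients are affected is unknown. The endpoints are exploratory and the primary EAR analysis is unaffected.

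The home-definition gap is secondary. A single recorded fall of 15-30% may not qualify, the direction of the 1-hour window is undefined, and throat tightness is not among the protocol's chest items.

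Two stronger readings are tempting and should not be drawn:
- **That home LARs are shown to be under-counted.** On the same readings the confirmed definition cannot count more events than a bare 15% fall, but some falls it removes may be false. The documents give neither a home LAR rate nor a detection rate.
- **That sleep gaps bias the arms.** A later exit moves the sleep gap earlier on the LAR clock (hours 10-18 rather than 13-21 after exit, on the clock times assumed in step 5). No direction or size of bias follows without knowing when LARs occur.

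**What to change.** In SAP 5.6.3:
1. Censor time to LAR and time to any asthmatic reaction at the last valid FEV1 reading within 24 h of EEU exit.
2. For both Fisher's tests, report by arm how many patients lack home readings, and add a sensitivity analysis excluding them.
3. Treat overnight gaps followed by resumed readings as interval-censored in a sensitivity analysis.
4. Keep the confirmed home definition as the main one. Add a sensitivity analysis that counts any home fall of at least 15% with rescue use or a positive adjacent chest-symptom entry.
5. State how the second effort is obtained at home and whether the 1-hour window is two-sided, and align the symptom items with Protocol 8.2.2.3.

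The cost is wording, minor programming and slightly shorter follow-up for some patients. Censoring at the last reading assumes that stopping is unrelated to LAR risk, so the counts in item 2 should be read alongside the result. SAP section 1 allows revision on blinded review before data lock.
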